### 5.1.2 Spirometry

#### General requirements

Pulmonary function will be measured by spirometry at the study site using equipment provided by a central vendor. Spirometry will be performed by the Investigator or authorized delegate according to American Thoracic Society/European Respiratory Society (ATS/ERS) guidelines ([Miller et al 2005](#)).

The vendor providing central spirometry services will be responsible for assuring that the spirometer used by each site meets ATS/ERS recommendations, and that the study site personnel who will be performing the testing are properly certified. Spirometry calibration will be detailed in a separate spirometry procedures manual.

#### Time of day for scheduled site visit spirometry

For adult subjects, spirometry testing must be initiated in the morning between 6:00 AM and 11 AM according to the schedule provided in Table 1. For adolescent subjects, spirometry testing can be initiated during the whole day according to the schedule provided in Table 1. All post-randomization spirometry assessments should be performed within  $\pm 1.5$  hours of the time that the randomization spirometry was performed.

**Subjects should be instructed not to use their maintenance twice daily LABA (or ICS-LABA) within 12 hours of the scheduled site visit spirometry** as this will affect the pre-BD FEV1 value; they may be taken subsequently at the site. For theophylline and once daily BDs a 48 hour washout period is required. **For the same reason, subjects should not use their**

**SABA within 6 hours of scheduled spirometry/dECG assessments.** This restriction is particularly critical for efficacy measures taken during the treatment period, but should also facilitate meeting the run-in FEV1 and reversibility eligibility criteria.

Options for handling subjects who have inadvertently taken their asthma medication within the restricted window are described in section 7.7.2.

Subjects that have a spirometry assessment at an unscheduled visit due to a worsening of asthma do not need to follow the washout instructions.

### **Spirometry technique**

Subjects should avoid engaging in strenuous exertion for at least 30 minutes prior to spirometry measurements. Subjects should avoid eating a large meal for at least 2 hours prior to spirometry measurements at the site. All spirometry manoeuvres (irrespective of whether to obtain values for FEV1, FVC, FEF 25-75%) should be performed with the subject seated in an upright position. If this is not comfortable for the subject, standing is permitted. The same position should be used by the subject for each forced expiratory manoeuvre from enrolment throughout the study. The head must not be tilted during manoeuvres and the thorax should be able to move freely; hence tight clothing should be loosened. A nose-clip should be used for the manoeuvre. Mouthpieces of the same dimension and shape should be used by the subject from enrolment throughout the study.

The spirometry manoeuvre consists of three phases; the first is maximal inspiration, the second is a “blast” of exhalation (to obtain the FEV1 value) and the last is a continuation to complete exhalation. The subject should inhale rapidly and completely from functional residual capacity. It is important that the preceding inspiration is fast and that any pause at full inspiration be minimal (i.e. only for 1-2 seconds). The subject should be prompted to “blast”, not just “blow”, and they should be encouraged to fully exhale until the end of test criteria are met. If the patient feels dizzy, the manoeuvre should be stopped, since syncope could follow due to prolonged interruption of venous return to the thorax. Manoeuvres that do not meet the end of test criteria should not be used to satisfy the requirement of three acceptable manoeuvres. However early termination, by itself, is not a reason to eliminate all the results from such a manoeuvre from further consideration.

To allow recording of the FVC value, it is important that the whole manoeuvre lasts for at least 6 seconds. Ensure that none of the following has occurred: coughing during the first second, glottis closure, leak or obstruction of the mouthpiece (by the tongue).

Multiple forced expiratory efforts (at least 3 but no more than 8) will be performed for each spirometry session. There should be at least 3 efforts that meet ATS/ERS acceptability criteria with the highest value and second highest value for FEV1 and FVC meeting the ATS/ERS reproducibility criteria. The largest FVC and the largest FEV1 should be recorded after examining the data from all of the usable curves, even if they do not come from the same curve. If the criteria for acceptability and reproducibility are not met with the first 3

expiratory efforts, then additional attempts are required up to a maximum of 8. If the reproducibility criteria is not fulfilled after the maximum number of manoeuvres has been performed, the highest of the FEV1 and FVC value that is deemed acceptable should be selected. The absolute measurement (for FEV1), and the percentage of PNV (Quanjer et al 2012) will be recorded.

The mean forced expiratory flow between 25% and 75% of the FVC (FEF25–75%) is taken from the blow with the largest sum of FEV1 and FVC. The FEF25–75% must be measured with an accuracy of at least +5% of reading or +0.2 L whichever is greater. It is highly dependent on the validity of the FVC measurement and the level of expiratory effort.

### **Order of administration of usual asthma controller medication and IP relative to scheduled pre-and post-BD spirometry.**

When spirometry is performed the subject's usual asthma controller medication, BD and IP dose, should be withheld until after the final post-BD spirometry are complete.

### **Record keeping**

A signed and dated copy of the pre- and post- BD printout must be kept at the study site for source data verification. The printout must be marked with the study code, subject enrolment code, date and time of measurement, and visit number.

### **Spirometry references**

The Global Lung Function Initiative (GLI) equations will be used to determine the subjects PNVs and are pre-programmed into the spirometer (Quanjer et al 2012).

FEV1, expressed as percent of the PNV, will be calculated as follows:

$$\text{FEV}_1\% \text{ of PNV} = (\text{FEV}_1 \text{ measured} / \text{FEV}_1 \text{ PNV}) \times 100$$

#### **5.1.2.1 Reversibility test and post-BD FEV1 efficacy assessment**

The initial (pre-BD) FEV1 measurement (Section 5.1.2) must be completed before commencing the post-BD assessment.

As before, ensure that the subject has withheld each of their theophylline and BD medications for the minimum period of time specified in Section 7.7.2 and Appendix H. If the subject did not withhold their medications as specified, the reversibility assessment should be re-scheduled within the next 7 days; other visit assessments may be completed as planned.

Albuterol 90µg metered dose or Salbutamol 100µg metered dose will be used in the reversibility assessment. Up to 8 doses may be administered at Visit 2 and Visit 3, and up to 4 doses at the other visits (Visit 7, Visit 29 (EOT) and/or IP Discontinuation Visit). The dose should be adjusted if there is any concern about the effect on the subject's heart rate, tremor or any other safety parameter during the assessment; the reason should be noted in the subject's medical records.

A spacer device should be used for administration of the SABA; nebulizers should not be used. The same bronchodilator and type of device should be used at each visit where reversibility is assessed.

**Step 1: FEV1 measurement after 4 SABA inhalations**

For administration of albuterol/salbutamol, the subject will:

- (i) Perform a gentle, complete expiration
- (ii) Inhale Dose 1 of the SABA to TLC and hold their breath for 5-10 seconds before the subject exhales.
- (iii) Rest for approximately 30 seconds before the next dose
- (iv) Repeat this for Dose 2, Dose 3 and Dose 4, resting for a further 15 – 20 minutes after Dose 4

After resting for 15 – 20 minutes, proceed to measure FEV1 following the technique described in Section 5.1.2

Visit 2 and Visit 3: if the inclusion criterion for reversibility is met ( $\geq 12\%$  and  $\geq 200$  mL) this is the end of the reversibility assessment. If it is not met the subject proceeds to Step 2.

Visit 7, Visit 29/EOT and/or IP Discontinuation Visit: this is the end of the reversibility assessment.

**Step 2: FEV1 measurement following a further 2 (total of 6) SABA inhalations (Only at Visit 2 and Visit 3, if assessed)**

The subject will repeat the SABA inhalation procedures for Dose 5 and Dose 6. (See Step 1 above for instructions.)

After resting for 15 – 20 minutes FEV1 will be measured following the technique described in Section 5.1.2.

This is the end of the reversibility assessment if either of the following occurs:

- the inclusion criterion for reversibility is met ( $\geq 12\%$  and  $\geq 200$  mL) or
- the incremental change in FEV1 between Step 1 and 2 is  $\leq 5\%$  and the inclusion criterion is not met

Subjects proceed to Step 3 if the incremental change in FEV1 between Step 1 and Step 2 is  $> 5\%$  and if the criterion for reversibility has not yet been met.

**Step 3: FEV1 measurement following a further 2 (total of 8) SABA inhalations (Only at Visit 2, and Visit 3 if assessed)**

The subject will repeat the inhalation procedures for Dose 7 and Dose 8, resting for 15 – 20 minutes after Dose 8. (See Step 1 above for instructions).

After resting for 15 – 20 minutes, proceed to measure FEV1 following the technique described in Section 5.1.2. The reversibility assessment is now complete.

**For subjects who need to perform step 2 and/or step 3 of the reversibility testing at visit 3, the base-line value for the post-BD outcome variable in FEV1 will be derived from the value obtained after step 1.**

**5.1.3 Home PEF testing**

An electronic, hand-held spirometer (peak flow meter) will be dispensed to the subject at Visit 2. Home PEF testing will be performed by the subject in the morning upon awakening (and prior to taking their AM asthma controller) and in the evening at bedtime (and prior to taking their PM asthma controller). Recording of home PEF should start from the evening of Visit 2 (Week -2) until the morning of Visit 29 (Week 52) using an ePEF meter device. When possible, ambulatory lung function measurements should be taken at least 6 hours after the last dose of SABA rescue medication.

Subjects should perform 3 successive peak flow manoeuvres while sitting or standing, but in the same position at every testing; the highest of the 3 values will be captured for the morning and for the evening manoeuvres.

The investigator/authorized delegate will check subject's adherence to correct use of the peak flow meter at each visit as shown in [Table 1](#) (or on EOT visit if prematurely discontinued from the study).

**5.1.4 Periostin**

An investigational use only (IUO)/performance evaluation only (PEO) assay is being specifically developed and validated as a companion diagnostic for tralokinumab to address the potential identification of a target population with an enhanced response rate based on the presence of high serum periostin as an indicator of IL-13 driven asthma. The performance characteristics of the periostin assay have not been established. No clinical decision or patient notification should be made based on the results obtained with this product.

A baseline periostin concentration level using the investigational assay will be determined for each subject enrolled in the trial. Subject assessment with regards to periostin baseline level at Visit 2, will be used for stratification purposes. Analysis will be performed by the central laboratory. Blood samples will also be obtained at Visits 3, 9, 16, and 29. These samples may be used in existing and/or future clinical studies of in vitro diagnostic assays.

Instructions for sample collection, processing, storage, and shipment will be included in a separate laboratory manual provided to the sites.

### **5.1.5 Level of fractional exhaled nitric oxide**

#### **Method of assessment**

Fractional exhaled nitric oxide (FENO) measurements will be performed at Visits 1, 3, 5, 7, 16, 23, and 29 (see [Table 1](#)). Subjects should not use their rescue SABA medication (e.g., albuterol/salbutamol) within 6 hours of the measurement. Inhaled BDs (including ICS-LABA) should be withheld for the effect duration specific to the BD. If not, the visit must be rescheduled.

Measurements will not be performed until 2 weeks after a respiratory infection. Subjects will be asked whether they have had a respiratory infection in the 2 weeks prior to measurement, which will be recorded as “Yes or No” in the eCRF. Measurement of (FENO) will be performed prior to the spirometry measurements.

FENO will be measured using an electrochemical sensor. Information concerning the specifications and use of the analyzer will be provided in a separate instruction manual.

The standard single exhalation technique recommended by the ATS will be followed ([Dweik et al 2011](#)).

Signed and dated printouts from the measurements will be kept in the ISF for Source Data Verification (SDV). Printouts will be marked with the study code, subject enrolment/randomization code, date, time of measurement, visit number and subject initials. If a printout cannot be printed, the mean value of the measurements will be recorded in the subject’s medical records for SDV.

The vendor supplying the chemiluminescence analyzer to participating sites will be responsible for ensuring that the equipment and procedures for the measurement of FENO are validated prior to the start of the study.

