## 1. INTRODUCTION

### 1.1 Background and rationale for conducting this study

Asthma is a syndrome characterized by airway inflammation, reversible airway obstruction and airway hyper-responsiveness, with a global prevalence of approximately 300 million patients (GINA 2012).

Approximately 5% to 10% of asthma patients have severe asthma, many of whom may be inadequately controlled by inhaled corticosteroids (ICS) and long-acting  $\beta_2$ -agonists (LABA) in combination with additional controller therapies (Bateman et al 2010). These patients are at risk of asthma exacerbations, have a large medical need, and represent the greatest economic burden (Accordini et al 2006).

The observed variability in clinical response to currently available asthma therapies appears to be related, in part, to distinctive inflammatory phenotypes (Wenzel 2012). There is considerable evidence that interleukin-13 (IL-13) is a key mediator in the pathogenesis of asthmatic disease. IL-13 is secreted predominantly by CD4+ T-helper 2 (Th2) cells and IL-13 receptors are expressed on a number of cell types including those involved in the pathogenesis of asthma (Hershey 2003). There is evidence to support that IL-13 can increase development of airway hyper-responsiveness (Wardlaw et al 1988), potentiate bronchoconstriction (Grunstein et al 2002), increase the number of mucus-secreting cells and promote airway fibrosis in asthma (Wills-Karp et al 1998).

Tralokinumab is a human recombinant monoclonal antibody (MAb) of the immunoglobulin G4 subclass that specifically binds human IL-13, blocking interactions with the IL-13 receptor. Tralokinumab is in development for the treatment of severe asthma. A phase 2a study (MI-CP199) provided evidence of improvement of lung function (forced expiratory volume in 1 second (FEV1)), following the addition of subcutaneous (SC) tralokinumab to standard asthma controller medications. Doses of 300 and 600 mg every 2 weeks of tralokinumab both resulted in comparable effects in FEV1 that were greater than that observed with a 150 mg dose (Piper et al 2013). Since low pre-bronchodilator (BD) FEV1 has been identified as a strong independent predictor of subsequent asthma exacerbations, it is plausible that the addition of tralokinumab will reduce the rate of asthma exacerbations in this population (Reddel et al 2009).

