## 2.4 Exploratory objectives

| Exploratory Objectives:   | Outcome Measures:   |
|---|---|
| 
To explore baseline periostin, DPP4, and other biomarkers that may be associated with up-regulation of IL-13, as predictive biomarkers for treatment of tralokinumab
 | 
Key outcome variable:
 
 
• The annualised asthma exacerbation rate up to Week 52 (key variable)
 
 
Other outcome variables:
 
 
• Percent change from baseline in pre-dose/pre-BD FEV1
 
• Change from baseline in bi-weekly mean daily asthma symptom score (combined daytime and night-time score as captured in the Asthma Daily Diary)
 
• Change from baseline in Standardised AQLQ (S) + 12
 
• Change from baseline in ACQ-6
 
 |
| 
To explore change from baseline of biomarkers that may be associated with up-regulation of IL-13, and possible correlation with clinical efficacy of tralokinumab
    | 
Biomarkers may include:
 
 
• Blood eosinophils
 
• DPP4
 
• FENO
 
• Periostin
 
• Total serum IgE
 
 
Other biomarkers may be considered.
  |
|    | 
 
■ 
 
■ 
 
■ 
 
■ 
 
■ 
 
  |

| Exploratory Objectives:   | Outcome Measures:  |
|---|--|
|  |  |

*Results from the exploratory analyses, if performed, may be reported separately from the Clinical Study Report.*

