### **3.6 Methods for ensuring blinding**

This is a double-blind study in which tralokinumab and placebo are visually distinct from one another. Neither the subject nor any of the investigator or sponsor staff who are involved in the treatment or clinical evaluation and monitoring of the subjects will be aware of the treatment received. Since tralokinumab and placebo are visually distinct, IP will be handled by an unblinded IP manager at the site and will be administered by an unblinded investigational site study team member who will not be involved in the management of study subjects. (This could be the same person).

Should an issue arise with the IP (e.g. damaged kit or syringe that has been assigned to a subject prior to administration, or any other unexpected event with the kit or syringe (e.g. a malfunction during IP administration) the unblinded IP manager at the site will contact a predetermined unblinded AstraZeneca site monitor (who is not otherwise involved in the project) to determine whether any specific actions are required.

A blinded AstraZeneca site monitor will perform IP accountability. In the event that the treatment allocation for a subject becomes known to the investigator or other study staff

involved in the management of study subjects, or needs to be known to treat an individual subject for an AE, the sponsor must be notified *immediately* by the investigator and if possible, before unblinding.

All packaging and labelling of IP will be done in such way as to ensure blinding for all sponsor and investigational site staff (other than the unblinded IP manager who will directly handle the pre-filled syringes).

The following personnel will have access to the randomization list:

- those carrying out the packaging and labelling of IP
- those generating the randomization list

The information in the randomization list will be kept from other personnel involved in the conduct of the study, and in a secure location until the end of the study.

No member of the extended study team at AstraZeneca, or any CRO handling data, will have access to the randomization scheme during the conduct of the study, with the exception of the Supply Chain Study Management department and the Patient Safety department at AstraZeneca and personnel at the bioanalytical lab performing the PK sample analysis.

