## **4.2 Treatment period**

Inclusion criteria at randomization will be confirmed at Visit 3. Before randomization the subject's compliance with their usual asthma controller ICS-LABA and other asthma controller medication, and ePRO completion must be confirmed (see section [3.1](#), inclusion criteria [18](#) and [19](#)).

Subjects confirmed as eligible will be randomized at Visit 3 (Week 0) in a 1:1 ratio (i.e. 385 subjects on tralokinumab, and 385 subjects on placebo). Subjects will be administered tralokinumab 300mg or placebo via subcutaneous injection at the study site Q2W for a total of 26 doses.

The first dose of the IP will be administered following randomization through IWRS/IVRS at Visit 3.

Following randomization the subject will receive 52 weeks of double-blind treatment, with the last dose of tralokinumab/placebo administered at Visit 28 (Week 50).

Subjects will have scheduled visits at 2-week intervals to complete protocol-specific assessments and IP administration, as listed in [Table 1](#). Restrictions as set out in section [7.7.2](#) will continue to apply throughout the treatment period. In case of an asthma worsening/exacerbation (see section [5.1.1](#)), subjects should be evaluated at the study site,

when feasible, at an unscheduled visit, or ordinary visit if the worsening happens to fall within a scheduled visit window.

Subjects will continue to measure their PEF at home, as well as record asthma symptoms and responses to questionnaires in the Asthma Daily Diary throughout the 52-week treatment period (see section 5.2.2 for details).

Subjects will have brief physical exams performed at times listed in Table 1. A complete physical exam will be performed at Visit 29 (Week 52).

Additional blood samples will be obtained from the subjects at Visits 3, 9, 16 and 29 to further explore the relationship between the clinical response of tralokinumab and biomarkers.

The subject's adherence for completing all questionnaires in the ePRO will be assessed at all visits during the treatment period, with retraining provided as required.

At Week 52 subjects will come to the site for the End of Treatment (EOT) visit. The subject should bring the ePRO device to the EOT visit and complete the ACQ-6, AQLQ(S)+12, EQ-5D-5L, and the WPAI + CIQ, unless they have been completed at home prior to the visit.

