#### **5.2.2.7 Clinical – Global Impression of Change (CGIC) assessment**

The Clinical Global Impression of Change (CGIC) instrument is used to evaluate the overall response to treatment. The investigator (clinician) will be asked to rate the degree to which the overall asthma status may have changed when compared to baseline (i.e. randomization visit/initiation of study drug). The assessment uses a 7-point rating scale: 1 = Very Much Improved; 2 = Much Improved; 3 = Minimally Improved; 4 = No Change; 5 = Minimally Worse; 6 = Much Worse; and 7 = Very Much Worse.

The CGIC will be completed at the site visits as indicated in [Table 1](#). It is recommended that the same clinician completes the CGIC at all applicable visits for an individual subject. Before making the assessment the clinician will need to access and review the results from all relevant assessments including lung function measurements (FEV1 and PEF) and patient reported outcomes (Asthma Daily Diary, ACQ-6 and AQLQ) performed before the visit, Adherence to the patient reported outcomes should be closely monitored.

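### FeNO after randomization, a possible marker of the drug's target, is left open at the site and could give blinded staff a partial clue to allocation

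*Protocol*

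**What the plan says.** **Measurement.** Section 5.1.5 states that FeNO "measurements will be performed at Visits 1, 3, 5, 7, 16, 23, and 29". Section 4.2 fixes the start of treatment: "The first dose of the IP will be administered following randomization through IWRS/IVRS at Visit 3". The analyzer is supplied to the sites. On the results, section 5.1.5 says "Signed and dated printouts from the measurements will be kept in the ISF for Source Data Verification (SDV"; where no printout can be made, the mean value is entered in the subject's medical record. It does not say who reads or signs the printout.

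**Link to the drug.** Section 1.1 says that tralokinumab "specifically binds human IL-13, blocking interactions with the IL-13 receptor". Section 2.4 names FeNO under the objective "To explore change from baseline of biomarkers that may be associated with up-regulation of IL-13, and possible correlation with clinical efficacy of tralokinumab".

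**Blinding.** Section 3.6 sets the standard: "Neither the subject nor any of the investigator or sponsor staff who are involved in the treatment or clinical evaluation", or in monitoring, may know the treatment received. Its measures concern the visibly different product, the randomization list, access to the allocation scheme, and notification if allocation becomes known. The only unblinded site role is handling and giving the product. FeNO is not mentioned.

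**Endpoint.** Under section 5.1.1, worsening asthma that leads to at least 3 days of systemic corticosteroids is an exacerbation. Events without any objective support are not counted. Under section 6.8.1, a blinded committee adjudicates ER or urgent care visits, hospitalizations and deaths. Steroid-only events are not listed.

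**Instrument.** Section 5.1.5 says FeNO is measured with an electrochemical sensor, and then: "The vendor supplying the chemiluminescence analyzer to participating sites will be responsible" for validating equipment and procedures.

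**The concern.** The drug blocks IL-13, and the protocol itself treats FeNO as a candidate readout of IL-13 activity. A subject's FeNO before and after dosing may therefore carry information on allocation, and section 5.1.5 places those values in site files without restriction.

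This matters because a primary endpoint event can be a treatment decision. A clinician who suspects that a subject is on active drug may be slower to start steroids, and one who suspects placebo may be quicker. Either would move the exacerbation rate ratio with no drug effect behind it.

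Periostin is handled differently. Section 5.1.4 sends it to a central laboratory and bars clinical decisions or patient notification based on the result. The reason given there is the unproven assay rather than blinding, but the effect is protective, and FeNO has no equivalent rule.

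**Working it through.** The plan states no figure on this point, so the check is mainly a comparison of sections.

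**1. Which readings count.** FeNO visits (section 5.1.5): 1, 3, 5, 7, 16, 23, 29, which is 7. The first dose is at Visit 3. FeNO precedes spirometry (section 5.1.5), and product is withheld until spirometry is finished (section 5.1.2), so the Visit 3 reading is before dosing. Readings after the first dose: 7 − 2 = 5. Section 8.4.2.1 ends follow-up for the primary endpoint at Visit 29, so that reading cannot affect a counted event: 5 − 1 = 4, at Visits 5, 7, 16 and 23 (Weeks 4, 8, 26 and 40). Events before Week 4 cannot be affected, which leaves at most 52 − 4 = 48 weeks exposed.

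**2. Who can see the value.** The only unblinded site role (section 3.6) is limited to the product. FeNO printouts in the site file and values in the medical record are therefore within reach of staff who treat, assess or monitor. That is an inference, since no signatory is named.

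**3. What an existing protection catches.**

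| Route to an event | Objective-support rule (5.1.1) | Blinded adjudication (6.8.1) |
|---|---|---|
| Hospitalization, ER or urgent care visit | yes | yes |
| Steroid course only, recorded without support | removed | not listed |
| Steroid course only, recorded with support | stays counted | not listed |
| Steroid course not given because active drug is suspected | cannot restore it | never reaches the committee |

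The last two rows are the residual exposure.

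**4. How much one reading could reveal (assumption).** The protocol gives no FeNO effect. Suppose FeNO change is normal with equal spread in both arms and the arm means differ by d standard deviations. With 1:1 allocation the best cut-off is midway, and the chance of guessing the arm correctly is Φ(d/2):

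| assumed d | 0 | 0.2 | 0.5 | 0.8 | 1.0 | 1.5 |
|---|---|---|---|---|---|---|
| correct guess | 50% | 54% | 60% | 66% | 69% | 77% |

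At d = 0 there is no clue. Even at d = 1.5, almost one guess in four is wrong (100% − 77% = 23%).

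**5. Whether masking removes anything needed.** FeNO appears in no eligibility criterion (3.1, 3.2), no discontinuation criterion (3.9.1) and no rule for rescheduling a dose (7.2).

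**6. Instrument.** An electrochemical sensor and a chemiluminescence analyzer are different technologies. Read literally, the validation duty attaches to a device other than the one said to be used.

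**The case against.** The strongest reply is that the protocol is silent on masking rather than wrong. It leaves use of the analyzer to a separate manual, where display rules could sit. That is fair, but section 5.1.5 itself fixes printouts at the site and a medical-record fallback, and a manual would have to override it.

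Several stronger readings are tempting, and the protocol does not support them:

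- **That FeNO reveals allocation.** No FeNO effect is given, and the link to IL-13 is worded as a possibility under an exploratory objective. A partial clue is the most that can be said.
- **That blinded staff are stated to sign the printouts.** The signatory is not named.
- **That section 3.6 guards only against seeing the syringe.** It also covers the randomization list, the allocation scheme and notification.
- **That the CGIC rater must use FeNO.** Section 5.2.2.7 says "Before making the assessment the clinician will need to access and review the results from all relevant assessments", but then names lung function and patient-reported outcomes, not FeNO. FeNO is neither required nor excluded, and CGIC is outside the testing hierarchy of section 8.5.1.
- **That total IgE raises the same problem.** No section says IgE results are reported to sites.
- **That the rate ratio is biased by a stated amount.** This would need a second assumption, on how far suspicion changes prescribing, for which the protocol gives no basis.

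Two further limits stand. Section 5.1.1 foresees exacerbations treated away from the study site, so not every steroid decision is made by staff who could see FeNO. Blood eosinophils, from the same list in section 2.4, and FEV1, which section 1.1 says improved on the drug, also stay visible. Masking FeNO reduces the clue and does not remove it.

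**Conclusion.** The point holds as a gap in the blinding provisions. FeNO after randomization is open at the site, the protocol regards it as a possible marker of the drug's target, and nothing masks it from staff whose steroid decisions can become primary endpoint events. Four readings are relevant, at Visits 5, 7, 16 and 23. The exposure is confined to steroid-only events and depends on FeNO changing on active drug, which the protocol does not quantify. One reading would identify the arm 50% to 77% of the time over assumed differences of 0 to 1.5 standard deviations. No size for any bias in the rate ratio can be derived.

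This is a cheap improvement and not a defect that undermines the primary analysis. The conflict over the FeNO instrument is a separate wording error. It rests on no assumption and has no bearing on blinding.

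**What to change.** In section 5.1.5, and by reference in section 3.6:

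1. After Visit 3, withhold FeNO values from subjects and from site and sponsor staff who treat, assess or monitor them. Mask the device display and printout, and upload results directly to the vendor. Readings at Visits 1 and 3 precede dosing and can stay open.
2. State that FeNO is not available for clinical or CGIC assessment during treatment.
3. Name the FeNO technology actually used and attach the vendor's validation duty to it.

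Having the unblinded product staff take the reading is not a good alternative: it puts someone who knows the allocation in charge of a measurement listed under efficacy assessments.

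The cost is a device or vendor setting, manual wording, and a change to source verification, because the printout in the site file would no longer serve. Section 9.4 already provides for reconciling third-party data. The residual clue from eosinophil counts and FEV1 remains.
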